8.2.9 Post Vaccination Symptom Log

Participants will be given a “Post vaccination symptom log” to use as a memory aid for tracking adverse events that occur during the 3 days following the injection. Participants will record daily temperature and systemic symptoms.

1. For this study, solicited AEs occurring during the 3 days after the vaccine/placebo injection will include:
 - unusually tired/feeling unwell
 - muscles aches
 - headache
 - chills
 - nausea
 - joint pain
2. Instruct participants to take their temperature at least once daily, starting with the day of injection (Day 0), after leaving the clinic and through Day 3 post-injection.
3. Temperature should be taken orally in the evening whenever possible. If more than one measurement is made in a day (for example due to feeling unwell), then the highest temperature taken that day should be recorded.
4. The symptoms and assignment of grades will be reviewed with participants to assure an understanding of how to use and evaluate each symptom during these first 3 days.

The study coordinator will discuss the symptom logs for accuracy and completeness at Day 2 and review and collect the completed symptom log at the Day 7 Visit. The study coordinator will review symptoms with participants for each identified symptom and clarify the grading assigned at the time. Additionally, active solicitation of AEs will be done at every visit. Participants will also be asked to contact the study coordinator, study PI, or designee should they experience any adverse events at any time points during the study.

8.2.10 *Solicited AE Assessments:*

The study coordinator will assess for Solicited AEs (expected) symptoms at Day 2 and Day 7 following each injection.

Assessments will consist of a standard series of questions administered at approximately 48 hours post vaccination (Day 2) and at the Day 7 Visit. The following local reaction evaluations ([Table 9](#)) and systemic reaction evaluations ([Table 10](#)) are part of each assessment.

Table 9 Local Reaction Solicited AE Assessments

Injection site erythema (redness)	Injection site pruritus (itching)
Injection site tenderness	Injection site swelling

Warmth at injection site	Skin discoloration
Injection site pain	Skin damage (vesiculation or ulceration)
Induration (hardening or formation of a crust or scab)	

Table 10 Systemic Reaction Solicited AE Assessments

Vomiting	Fatigue (extreme tiredness)
Malaise	Headache

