8.3.4 Adverse Event Reporting

Adverse events will be graded according to the DAIDS Table for Grading the Severity of Adult and Pediatric Adverse Events (DAIDS AE Grading Table), corrected Version 2.1, July 2017, on the DAIDS RSC website at <http://rsc.tech-res.com/clinical-research-sites/safety-reporting/daids-grading-tables>.

The study will monitor participants for adverse events. Toxicities will be characterized in terms including duration, intensity, and time to onset. Safety endpoints will include all adverse experiences, in addition to laboratory safety assessments, and vital signs. All AEs will be recorded on the appropriate study form.

AEs will be recorded in the database if any of the following criteria have been met:

- Study-related Grade ≥ 1 AEs
- Grade ≥ 3 AEs
- Autoimmune-related AEs regardless of grade
- HIV viral loads ≥ 50 copies/mL
- Injection reactions regardless of grade
- AEs that led to a change in study intervention regardless of grade
- AEs meeting SAE definition or EAE (Expedited Adverse Event) reporting requirement

Grade 1 or 2 Toxicity

Participants who develop a Grade 1 or 2 AE or lab toxicity that occurs following a vaccine/placebo injection that is thought to be possibly, probably, or definitely related to the study treatment should be discussed with the study team. Grade 1 or 2 AEs that may be related to the vaccine/placebo injection will be handled according to standard clinical practice and documented.

Grade 3 Toxicity

For participants who develop a Grade 3 AE following the administration of vaccine/placebo judged by the study PI (or designee) to be at least possibly study treatment-related, the protocol team must be notified within 24 hours. Participants experiencing Grade 3 AEs should be followed closely and if the AE does not return to

Grade ≤ 2 within 2 weeks, the study team should again be notified within 24 hours and the SMC will be notified.

For participants who experience a Grade 3 AE judged not related to the study treatment by the investigator, continued study participation is at the discretion of the study PI (or designee) in consultation with the protocol team and SMC.

Grade 4 Toxicity

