For participants who develop a Grade 4 AE following administration of vaccine/placebo judged by the study PI (or designee) to be at least possibly study treatment-related, the protocol team and SMC must be notified within 24 hours. Participants experiencing Grade 4 AEs should be followed closely with additional clinical assessments and laboratory testing as clinically indicated. If the AE does not return to Grade ≤ 2 within 2 weeks, the protocol team and SMC should again be notified within 24 hours.

All study treatments will be discontinued in the event of Grade 4 AEs possibly related to study treatment.

Local or Systemic Reactions to Vaccine/Placebo Injections

Grade 1 or 2

Local reactions of mild (Grade 1) or moderate (Grade 2) severity will usually resolve spontaneously. If needed, they may be managed with local application of cold packs, oral acetaminophen, oral non-steroidal anti-inflammatory agents, or a combination of these measures as appropriate.

NOTE: Topical steroids should not be applied to the injection site.

Grade 3 or 4

For severe (Grade 3) or potentially life-threatening (Grade 4) local reactions, the protocol team must be notified within 24 hours. For Grade 4 local reactions, definitive medical and/or surgical intervention should be undertaken as appropriate.

Systemic Reactions

The protocol team must be contacted within 24 hours for any non-local Grade 3 or 4 systemic reactions thought definitely, possibly, or probably related to the vaccine/placebo injections.

The common systemic adverse events usually seen with MVA vectored vaccines, **M3** and **M4**, include headache, feverishness, myalgia, arthralgia, fatigue, malaise, nausea, transient

flu like illness within 24 hours of vaccination, which usually resolves within 48 hours. It is anticipated that the majority of systemic adverse events post vaccination will be mild in intensity. However, there is a possibility of moderate or severe headache or malaise.

If an adverse event of special interest (AESI) occurs (see section 8.3.8), the study coordinator, in collaboration with the study PI (or designee), will evaluate the severity and seriousness of the AE and the relationship to the study treatment, and will document the findings. The protocol team should be contacted within 24 hours of notification of any reactions thought definitely, possibly, or probably related to the vaccine/placebo injections.

Injection Site Reaction

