Injection Site Erythema or Redness and Injection Site Induration or Swelling will not be considered an AE if there is no interference with usual social and functional activities such that:

- Grade 1 is: 2.5 to < 5 cm in diameter OR 6.25 to < 25 cm² surface area;
- Grade 2 is: ≥ 5 to < 10 cm in diameter OR ≥ 25 to < 100 cm² surface area;
- Grade 3 is: ≥ 10 cm in diameter OR ≥ 100 cm² surface area OR Ulceration OR Secondary infection OR Sterile abscess OR Drainage;
- Grade 4 is: Potentially life-threatening consequences (e.g., abscess, exfoliative dermatitis, necrosis involving dermis or deeper tissue)

Allergic or Hypersensitivity Reactions

Record all allergic and hypersensitivity reactions with both grade severity and attribution. Serious allergic or hypersensitivity reactions (≥ Grade 3) that are deemed possibly related to the study treatment by the study PI (or designee) will be reported to the protocol team and SMC within 24 hours of notification and to the NIH/DAIDS, UNC IRB, FDA, and study product sponsors within 48 hours per their reporting requirements.

Dose Limiting Toxicity (DLT)

- Hematologic dose-limiting toxicity will be defined as any confirmed toxicity ≥ Grade 2, that cannot clearly be attributed to another reversible cause.
- Follow participants per protocol schedule of events until the lab abnormality or toxicity resolves to ≤ Grade 1 or the participant's baseline.

- Non-hematologic dose-limiting toxicity will be defined as any confirmed symptomatic \geq Grade 3, if related (definitely, probably, or possibly) to vaccine/placebo.

Monitoring HIV RNA levels

In the event of viremia of \geq 50 copies/mL the following should occur per standard of care:

- Adherence to ART should be carefully assessed and documented.
- A standard HIV RNA assay should be repeated within 1-4 weeks.
- HIV resistance testing will be performed at the time of drawing a confirmatory sample and as indicated for persistent viremia.
- For HIV RNA confirmed >200 copies/mL on repeat testing, stored samples may be tested for the presence of one or more ARV drugs in the participant's regimen.
- HIV RNA will be repeated every 2 weeks, or sooner as clinically indicated, until <50 copies/mL and the participant can continue on study.

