8.3.7 Events of Special Interest

An adverse event of special interest (AESI; serious or non-serious) is one of scientific and medical concern specific to the protocol team, for which ongoing monitoring and rapid communication to the protocol team is required. These events might warrant further investigation in order to characterize and understand it. Depending on the nature of the event, rapid communication by the protocol team to the UNC IRB, FDA, NIH, and product manufacturers (i.e., regulators) might also be warranted.

AESI for this protocol include those listed below.

- Grade 3 or higher Injection site reactions
- Immune-related AEs attributed to study treatment of any grade

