9.3.8 Safety Analyses

For the safety endpoints, we will describe all study treatment-related AEs through Day 28 (primary endpoint) and the end of study (secondary endpoint). AEs will be coded per the Medical Dictionary for Regulatory Activities (MedDRA). Events prior to treatment (e.g., due to study-related procedure) will be listed separately in an appendix to the final clinical study report. The following tables of AE data will be created to summarize the number and percent of participants who experience at least one event of each of the following types:

- Study treatment-related AEs by severity grade
- All SAEs (this may be a listing if there are few events)
- Study treatment-related SAEs
- Fatal AEs (this may be a listing if there are few events)
- AEs that result in study discontinuation or study treatment discontinuation
- AEs categorized as AESI
- AEs with severity Grade 3 or greater
- Study treatment-related AEs with severity Grade 3 or greater
- All treatment-related AEs with severity Grade 1 or greater

All of these tables will display the number and percent of participants that experience the given event and will display events by System Organ Class (SOC) and Preferred Term (PT). Events will be displayed alphabetically for SOC and in descending order of overall PT incidence within each SOC.

9.3.9 *Tabulation of Individual Participant Data*

Individual participant data will be listed by measure and time point.

9.3.10 *Exploratory Analyses*

Other objectives or exploratory analysis can be grouped into additional immunological measures and virologic measures.

Immunologic measures: Kinetic data will be analyzed by descriptive statistics and graphical displays. Other observed immunologic measurements such as virus inhibition may not be normally distributed or may be partially censored due to assay limits of quantification, and thus, an exact Wilcoxon signed-rank test will be used for within-participant comparisons.

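### The exemption of injection-site redness and swelling in Section 8.3.4 has no grade limit; read literally, it takes a related Grade 3 reaction out of the primary endpoint and out of the pause rule as worded in Section 10.1.6 (minor)

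*Combined protocol and SAP*

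**What the plan says.** Section 8.3.4, under Injection Site Reaction, states that erythema or redness and induration or swelling at the injection site "will not be considered an AE if there is no interference with usual social and functional activities". The same sentence leads into definitions of Grades 1 to 4. Grade 3 is a diameter of at least 10 cm or an area of at least 100 cm², or any of "Ulceration OR Secondary infection OR Sterile abscess OR Drainage". Grade 4 covers potentially life-threatening consequences.

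Other parts of the protocol bear on the same reactions:

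- Section 8.3.1 defines an AE broadly. An unfavorable, unintended sign that follows use of the product qualifies, with no test of functional interference.
- Section 8.3.7 lists "Grade 3 or higher Injection site reactions" among the adverse events of special interest.
- Section 8.3.4, under local reactions, says: "For severe (Grade 3) or potentially life-threatening (Grade 4) local reactions, the protocol team must be notified within 24 hours".
- The primary endpoint (Sections 1.1, 3 and 4.1) is the occurrence of at least one related AE of Grade 3 or higher through 28 days after vaccination. The only stated exclusion is a transient Grade 3 blood pressure rise during leukapheresis.
- Section 10.1.6 suspends enrollment under criterion (a) when two or more participants have a primary safety outcome that is a related Grade 3 or higher AE, and under criterion (b) when one or more have a possibly related SAE.
- Section 9.2.1 gives the same two-participant rule and refers to Section 10.1.6, but speaks of treatment-related toxicity of Grade 3 or above and does not use the term AE.

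**The concern.** The exemption tells staff how to classify an event. A reaction that is not an AE cannot be a Grade 3 AE, so it cannot be a primary endpoint event or count toward criterion (a). Yet Section 8.3.7 calls the same Grade 3 reaction an adverse event. Two people applying the protocol carefully to the same participant could reach different answers.

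This is a first-in-man trial with safety as its primary objective, 7 participants per vaccine arm, and a pause at two events. A single classification is visible in an arm's reported proportion and upper limit, and two could determine whether criterion (a) is met.

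**Working it through.** **Which texts conflict**

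1. The exemption covers only erythema/redness and induration/swelling, and only without functional interference. Pain, tenderness, systemic reactions and any reaction that limits activity are unaffected.
2. Within that scope, the sentence does not stop at Grade 2; the list under it includes Grades 3 and 4.
3. Section 8.3.7 at Grade 3 or higher, and Section 8.3.1 at any grade, make the same finding an adverse event. Neither has a functional condition.
4. The primary endpoint and criterion (a) in Section 10.1.6 require an AE. Under the exemption a related 12 cm area of redness with no limitation does not count; under Section 8.3.7 it does.
5. Section 9.2.1 requires a related toxicity of Grade 3 or higher. On that wording the 12 cm reaction counts toward the pause whether or not it is called an AE. Two such participants would therefore suspend enrollment under Section 9.2.1 but not under Section 10.1.6 read with the exemption.

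**What one event does to the primary estimate**

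The inputs are n = 7 per vaccine arm and the exact one-sided 95% upper binomial limit (Sections 9.2.1 and 9.3.3). For x events in n, the limit U solves P(X ≤ x | n, U) = 0.05.

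- x = 0, n = 7: U = 1 − 0.05^(1/7) = 34.8%. Section 9.2.1 states 35%.
- x = 1, n = 7: (1 − U)^7 + 7U(1 − U)^6 = 0.05 gives U = 52.1%. Section 9.2.1 states 52%.

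Both of the plan's figures are reproduced. If one exempt reaction occurs in an arm with no other event:

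| | Counted | Not counted |
|---|---|---|
| One arm | 1/7 = 14.3%, limit 52.1% | 0/7 = 0%, limit 34.8% |
| Three vaccine arms, n = 3 × 7 = 21 | 1/21 = 4.8%, limit 20.7% | 0/21 = 0%, limit 13.3% |

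The pooled 13% in Section 9.2.1 is labeled n = 24. It matches 0/21 (13.3%); 0/24 gives 11.7%. That is a separate correction and carries no weight here.

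**How likely it is**

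- With the earlier vaccine, Grade 3 events of all kinds occurred in under 5% of vaccinees (Section 2.2.4).
- Injection-site reactions in HIV-CORE 001 were all mild or moderate (Section 2.2.4).
- AEs in studies at 2 × 10^8 pfu are described as Grade 1 and 2 (Section 4.3).
- The moderate or severe AEs named in Section 2.3.1 do not include erythema or induration.

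The documents do not say what share of Grade 3 events would be large redness or swelling without limitation, and Section 2.3.1 says there is no human experience with M3 or M4. The chance is low, but no defensible upper bound can be calculated.

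**The case against.** The strongest reply is that the sentence is a garbled grading scale. Taken literally it would make a potentially life-threatening reaction a non-AE, which nobody can have intended, and Section 8.3.7 shows that Grade 3 or higher reactions were meant to count. That is probably the intent. However, the text does not say so, and the exemption is phrased as an instruction to those classifying events.

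A reader might draw several stronger conclusions. The documents do not support them:

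- **That Grade 3 reactions would go unseen.** The 24-hour notice applies to local reactions without asking whether they are AEs. The safety monitoring committee (SMC) receives monthly reports and can be contacted about any matter bearing on participant safety, and its response can suspend the study (Section 10.1.6).
- **That the pause rule fails.** Section 9.2.1 would count the event, and criterion (b) still responds to any possibly related SAE.
- **That ulcers, infections or abscesses drop out.** The exemption names only redness and swelling. "Table 9 Local Reaction Solicited AE Assessments" (Section 8.2.10) lists skin damage, including ulceration, as a separate item, and infection or abscess is an untoward occurrence in its own right under Section 8.3.1. The realistic gap is size alone.
- **That the solicited list and the recording rule are further contradictions.** Table 9 sets out what staff ask about. "Injection reactions regardless of grade" is one entry in a list of AEs to be recorded, so it presupposes an AE. The same holds for "AEs categorized as AESI" in Section 9.3.8. For that reason these two entries cannot establish that an exempt reaction would still be recorded and tabulated.
- **That the secondary safety endpoint is wrong.** Whether symptom-free Grade 1 or 2 redness counts there is a policy choice, and either answer is acceptable.

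**Conclusion.** The point holds and is minor. As written, Section 8.3.4 conflicts with Sections 8.3.7 and 8.3.1. Its literal consequence is that a related Grade 3 area of redness or swelling without functional limitation leaves the primary endpoint and criterion (a) of Section 10.1.6, while Section 9.2.1 would still count it toward a pause. The effect of one event is the 17.3-point difference in an arm's upper limit (52.1 − 34.8). This assumes that the event occurs within 28 days, is judged at least possibly related, is the only event in its arm, and is classified by the literal sentence. The protocol's experience with related vaccines suggests that this will be rare. A Grade 4 reaction with no functional effect is hardly realistic.

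**What to change.** In Section 8.3.4, state that the exemption applies to Grades 1 and 2 only. Add that an injection-site reaction meeting the Grade 3 or 4 criteria is an AE with or without functional interference and, if related, counts toward the primary endpoint and pause criterion (a). Use one wording for the pause rule in Sections 9.2.1 and 10.1.6.

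This takes a few sentences at the next amendment, needs no new data, and should be done before unblinding so that no classification is settled with arms known. The cost is that two participants with large, symptom-free redness would suspend enrollment until the SMC has reviewed them. If the sponsor does not want that, reactions graded 3 on size alone can be made an explicit exception in the endpoint definition and in both statements of the pause rule, as is already done for blood pressure during leukapheresis.

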8.3.6 Reporting Events to Participants

We are engaged in a number of similar studies of novel immunotherapies for HIV, persistent HIV infection, monoclonal antibodies, latency reversing agents, and other interventions. We report the scientific findings of our work in the literature, and have regular (annual or more frequent) presentations with the local and national HIV-infected and affected community. Due to the lack of evidence thus far that our studies have a clinical impact, we discuss the scientific findings in a general way with each participant after EOS visits. Our studies have extremely stringent stopping criteria, and thus far, we have had no relevant or study-related SAEs to report. We would inform all study participants by letter or electronic messaging of any AEs determined by the External Study Safety Monitoring Committee to merit such notice.

8.3.7 Events of Special Interest

An adverse event of special interest (AESI; serious or non-serious) is one of scientific and medical concern specific to the protocol team, for which ongoing monitoring and rapid communication to the protocol team is required. These events might warrant further investigation in order to characterize and understand it. Depending on the nature of the event, rapid communication by the protocol team to the UNC IRB, FDA, NIH, and product manufacturers (i.e., regulators) might also be warranted.

AESI for this protocol include those listed below.

- Grade 3 or higher Injection site reactions
- Immune-related AEs attributed to study treatment of any grade

8.3.8 Reporting of Pregnancy

If the participant becomes pregnant during the study, vaccine/placebo will not be administered. Although not considered an adverse experience, it is the responsibility of investigators or their designees to report any pregnancy in a participant or participant's partner (spontaneously reported to them) that occurs during the study or within 4 months after vaccination. All participants or their partners who become pregnant must be followed to the completion/termination of the pregnancy. If the pregnancy continues to term, the outcome (health of infant) must also be reported the UNC IRB, the DAIDS Medical Officer, and the FDA (US Food and Drug Administration).

If a male participant impregnates his partner while he is participating in this study, the pregnancy must be reported and the study PI (or designee) should make a concerted effort to follow the pregnancy and outcome. The study PI (or designee) will make every effort to obtain a medical release and a separate pregnancy outcome consent from the pregnant partner granting permission to follow the health of both the pregnant partner and her unborn child to the UNC IRB, DAIDS, study product sponsor, and FDA without delay and within 24 hours if the outcome is an SAE (e.g. death, abortion, congenital anomaly, or other disabling or life-threatening complication to the mother or newborn).

Pregnancy and pregnancy outcome will be recorded. Pregnancies that occur on study should be reported prospectively to the Antiretroviral Pregnancy Registry. More information is available at www.apregistry.com. [contact]; [contact].

Pregnancy Outcomes and Reporting

If a woman has completed the study or chooses to discontinue from the study before the end of the pregnancy, then site study staff should request permission via a separate pregnancy outcome consent to contact her regarding pregnancy outcomes at the end of pregnancy. If the information is obtained, pregnancy outcomes will be submitted at the end of the pregnancy.

Pregnant women will discontinue study treatment and will be encouraged to continue on study and complete the evaluations included in the post-treatment evaluation section. At the end of the pregnancy, outcome and adverse events for participant and infant will be recorded. If pregnancy is suspected in a woman on study after study treatment, then a pregnancy test should be obtained. If pregnancy is confirmed, then further study treatment will be discontinued and the woman should continue on study (off study product) safety follow-up visits as noted in the SOE. Stored plasma/PBMC for stored plasma for virologic studies should not be obtained to minimize blood volume.

The site study staff should request permission via a separate pregnancy outcome consent to contact her regarding pregnancy outcomes at the end of pregnancy. A visit 6 months

following the end of pregnancy will be conducted to assess for evidence of adverse events (AEs) in the participant and infant and documented.

